**The Effect of Synbiotic Tablet Usage on the Clinical and Biochemical
Parameters in Smokers and Nonsmokers with Gingivitis: A Randomized
Placebo-Controlled Clinical Trial**

Document Date: February 27, 2018

Study Design

This study designed as a double-blind randomized placebo-controlled clinical trial.

Participants were primarily divided into two groups according to their smoking and non-smoking status. Then both groups in itself were randomly assigned again into two groups as test and control groups. Randomization was performed by one researcher that had never any role in participant's treatment and clinical measurement processes ([name]). Random selection was made in first person's participation by coin toss and then next participant was included into the other group according to previous participant's group. Four groups in this study are shown below:

- Smoker(+), test group(T) given synbiotic tablets; (T(+))
- Smoker(+), control group(C) given placebo tablets; (C(+))
- Non-smoker(-), test group(T) given synbiotic tablets; (T(-))
- Non-smoker(-), control group(C) given placebo tablets; (C(-))

In the screening phase, clinical measurements were carried out as an initial evaluation and in the next visit biochemical and microbiological samples were collected for baseline examination and all participants were received mechanical debridement procedure including tooth-polishing (rubber-cup and abrasive paste) and scaling by the help of ultrasonic devices §§ and periodontal hand pieces ¶¶ before the experimental period. On the day of periodontal treatment each subject was instructed to chew one test or placebo tablet that was given according to their groups, per day, during 30 days. Test and placebo tablets were prepared to have the same characteristics in terms of shape, color, taste and size. Commercially available Probiotic Chewable Tablets ¶¶ (Table 1) were used in the test group and a placebo tablet had been prepared to same company with similar content with the test tablets but does not contain microorganisms. Oral hygiene training with tooth brush and floss was given to all participants. They were also instructed not to take other probiotic products throughout the test period. Clinical parameters including PI (28) and GI (29) and GCF samples had been obtained from all subjects on days 0 (baseline), 30 (1st month), and 60 (2nd month). Patients' professional supragingival plaque control was made in the control session of 1st and 2nd month. Side effects were recorded by patients'

verbal statement. Patients' all measurements and treatments were made by a single researcher who doesn't know in which group participants were included ([name]).

Biochemical Analysis

GCF samples were collected at baseline, 1st and 2nd months from contralateral upper or lower buccal region of canine or incisors having the most significant presence of inflammation and plaque accumulation. As once regions were determined at baseline, it wasn't changed in other evaluations. After removal of supragingival plaque from interproximal surfaces with sterile curettes, these surfaces were air-dried and isolated with cotton rolls before GCF collection. GCF samples were collected with paper strips ^{##}. Paper strips were inserted into the pockets until feeling a slight resistance and hold for 30 sec. Care had been taken to avoid any mechanical damage and strips were discarded when contaminated with blood samples. Strips were then transferred to the calibrated device of Periotron 8000***. GCF volume was recorded to a computer as μ l. Total of 4 strips taken from each individual were placed into eppendorf tube and first stored at -20°C, then at -80°C until the time of analysis. IL-6, IL-8, IL-10 levels of GCF were measured using commercial kits ^{†††} by using ELISA method. The standard test procedure according to the manufacturers' instructions was applied.

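### The trial is called randomised, but the only allocation rule stated is one coin toss followed by alternation, which is quasi-randomisation

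*Protocol*

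**What the plan says.** The protocol makes the claim of randomisation in three places. The title reads "Parameters in Smokers and Nonsmokers with Gingivitis: A Randomized" and continues as a placebo-controlled trial. The Study Design section opens with "This study designed as a double-blind randomized placebo-controlled clinical trial". After participants are divided by smoking status, it adds: "Then both groups in itself were randomly assigned again into two groups as test and control groups".

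The same paragraph then gives the mechanism. The first person was assigned "by coin toss and then next participant was included into the other group according to previous participant's group", so each next participant goes to the arm opposite to the previous participant's. Neither document, in the text available, mentions a random number list, blocks, envelopes or any other way of generating or concealing the sequence.

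Three safeguards are described in Study Design:

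- **Allocator:** "Randomization was performed by one researcher that had never any role in participant's treatment and clinical measurement processes".
- **Tablets:** "Test and placebo tablets were prepared to have the same characteristics in terms of shape, color, taste and size".
- **Researcher:** one researcher, unaware of group, made all measurements and gave all treatments. On the text this covers screening as well: "In the screening phase, clinical measurements were carried out as an initial evaluation".

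**The concern.** Random assignment is the central design claim, and readers will weigh the evidence by it. Under alternation the two arms of a stratum are simply the odd-numbered and even-numbered entrants, and the toss decides only which set receives the synbiotic. A fair test-versus-placebo comparison then depends on order of entry being unrelated to prognosis. That is an assumption, not something the design secures.

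Alternation is also easy to predict. If it ran within each smoking stratum, one known assignment plus the order of entry reveals every other assignment in that stratum. Anyone with that knowledge and some control over who enters, or when, could steer participants. Selection of that kind would affect every outcome, the plaque and gingival indices and the interleukins alike. Blinded measurement would not remove it, because it acts before measurement begins.

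**Working it through.** **Step 1: label against mechanism.** The statement that participants were randomly assigned names no procedure. The sentence with the coin toss is the only one that does. It ties the toss to the first person and makes each later assignment depend on the previous one, so the rule is systematic allocation with a random start.

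**Step 2: possible readings.**

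- *One toss per smoking stratum.* Favoured, because the text says each smoking group was itself divided. This is alternation.
- *One toss for the whole trial.* Also alternation. It fits the text less well and would not guarantee equal arms within a stratum.
- *A new toss for every pair.* This would be true randomisation in blocks of two. It is weakly supported, since the toss is attached to the first participant.

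**Step 3: inputs.** The Statistical Analysis section of the SAP gives at least 15 per group plus at least 5 for missing data, hence 15 + 5 = 20 per group. With two groups per stratum, 2 × 20 = 40 per stratum. With four groups, 4 × 20 = 80 in total. Both inputs are minimums and are treated here as the enrolled numbers.

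**Step 4: how much was left to chance.** Fixed assignments = total − number of tosses. Possible lists for a given order of entry = 2^(number of tosses).

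| Reading | Tosses | Fixed, of 80 | Possible lists | Fixed, of 60 (15 per group) |
|---|---|---|---|---|
| One per stratum | 2 | 80 − 2 = 78 | 2² = 4 | 60 − 2 = 58 |
| One overall | 1 | 80 − 1 = 79 | 2¹ = 2 | 60 − 1 = 59 |
| One per pair | 40 | 80 − 40 = 40 | 2⁴⁰ ≈ 1.1 × 10¹² | 60 − 30 = 30 |

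For comparison, a single stratum of 40 has 2 possible lists under alternation. In permuted blocks of four it would have 6¹⁰ = 60,466,176.

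**Step 5: predictability.** Take someone who knows all previous assignments in a stratum of 40 and guesses the next. Under alternation the first guess is right half the time and the other 39 always, so (0.5 + 39)/40 = 98.75% are expected correct. For permuted blocks of known size four, the chances of a correct guess at the four positions are 1/2, 2/3, 2/3 and 1, so (1/2 + 2/3 + 2/3 + 1)/4 = 70.8%. For blocks of two the figure is (1/2 + 1)/2 = 75%. These are worst cases. The protocol says the treating and measuring researcher did not know group.

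**Step 6: does the analysis compensate?** The SAP plans Kruskal-Wallis tests on the measurements at baseline and at months 1 and 2. If the baseline test is read as a comparison between groups, it can reveal imbalance only in the variables measured. It cannot exclude imbalance in unmeasured ones, so it is a partial check.

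**The case against.** The strongest reply concerns severity. To exploit alternation, someone who influences entry must learn an assignment, and the documents show no route by which the treating and measuring researcher could. The allocator was separate and the tablets matched. No subversion is shown and no bias can be quantified. The rule is openly stated in the same paragraph as the claim, so only a reader of the title or a later report would be misled. With a fair toss, each participant still had a one-half chance of either arm. Some of what seems absent, such as who decided eligibility, may have been in pages not available for review.

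Much of this stands. The safeguards lower the risk, the counts describe the rule and not any harm, and silence about enrolment or concealment supports a query and no more. The equal marginal chance is also correct, but what alternation lacks is unpredictability and independence between participants, and that is the protection the word randomised is taken to promise. The mismatch between label and rule lies within the text that is present. Separation of roles does not turn a fixed sequence into a random one.

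**Conclusion.** The concern holds. As written, the allocation is alternation after a single random start, and the documents claim a property that this rule does not have. On the most natural reading 78 of 80 assignments were fixed and 4 lists were possible; with one toss overall the figures are 79 and 2. This rests on the plain meaning of the coin-toss sentence and on enrolment at the planned minimum. With 15 per group the fixed counts are 58 and 59 of 60.

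Only if the toss was repeated for each pair would the label be correct, and the wording gives that little support. Confidence in the mismatch is high. Whether it biased any result, in which direction and by how much cannot be determined from the documents. The label needs correcting because every between-arm comparison leans on it and nothing in the SAP makes up for it.

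**What to change.** 1. State the rule used: one toss per smoking stratum, one overall, or one per pair.
2. If it was alternation, replace the terms for random allocation with *quasi-randomised (alternation)* in the title, the Study Design section and all reports. If it was one toss per pair, report randomisation in blocks of two.
3. State who judged eligibility and enrolled participants, who knew the sequence, and whether the allocator could influence order of entry.
4. Qualify between-arm conclusions by the risk of selection bias, and present the baseline comparison as a partial check only.

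This costs a wording change, a few sentences of disclosure and a less favourable design label. The past tense suggests that allocation is complete. Only if it is still open, replace alternation with a computer-generated list in permuted blocks of randomly varying size, stratified by smoking status and held by the existing allocator. The extra work is preparing the list and coded tablet containers; the available text does not say who packed or dispensed the tablets.

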**Document Date: February 27, 2018**

## Statistical Analysis

The suitability of the normal distribution of the variables in our study was evaluated with graphical and Shapiro-Wilks test. The median (minimum, maximum) was used to display the descriptive statistics of variables identified as an abnormal distribution. Number (n) and percentage values were given to show the distribution of categorical variables like gender.

Kruskal-Wallis non-parametric analysis of variance was used to examine if there has been any discrepancy in the values of the clinical and biochemical measurements at baseline, 1st month and 2nd month. Bonferroni correction with the dual comparisons were made to determine the group causing variations in the variables found significant differences as result of Kruskal-Wallis test.

For comparing the clinical, biochemical and microbiological measurements at baseline, 1 month and 2 months in each group (T(+) T(-), C(+), C(-)) Friedman non-parametric repeated measures analysis of variance was used. Bonferroni correction double comparisons were made in variables determined statistically significant differences from the result of the Friedman test.

G\*Power pack program\*\*\* was used in order to determine the number of samples used in the study. For the width effect f: 0.25, type-I error probability  $\alpha$ :0.05, type-II error probability  $\beta$ : 0.05 and power: 0.95, at least 15 sampling units have been calculated to include in the study for each group. At least 5 subjects were added for each group considering the missing data that was deemed to occur during the course of follow-up. Sample size calculation was attempted based on the primary outcome measure.

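### On the natural reading, GCF regions are picked as the most inflamed at the visit that also supplies the baseline GCF value, so the within-group Friedman tests may partly reflect regression to the mean

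*Protocol*

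**What the plan says.** The Protocol, under Biochemical Analysis, samples GCF from contralateral canine or incisor regions "having the most significant presence of inflammation and plaque accumulation. As once regions were determined at baseline, it wasn't changed in other evaluations". Four strips per person go into one tube, and IL-6, IL-8 and IL-10 are measured by ELISA.

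Under Study Design, the Protocol labels day 0 as baseline and places PI, GI and GCF sampling there and at days 30 and 60. The same section describes an earlier clinical visit: "In the screening phase, clinical measurements were carried out as an initial evaluation and in the next visit biochemical and microbiological samples were collected" for the baseline examination. All participants have debridement before the experimental period, oral hygiene training, and professional plaque control at months 1 and 2. One examiner, unaware of group, makes all measurements.

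In the SAP (Statistical Analysis), the comparison of baseline, month 1 and month 2 within each of the four groups is as follows: "Friedman non-parametric repeated measures analysis of variance was used", with Bonferroni-corrected pairs after a significant result. Kruskal-Wallis tests compare the groups at each visit.

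**The concern.** A region that looks worst on a given day is partly one that is persistently bad and partly one that is having a bad day. If the bad day also alters the fluid volume or cytokines collected then, the baseline GCF value is off its usual level for that region. Because the region is then fixed, later samples return towards the usual level without any treatment having caused it. The Friedman tests and their pairwise follow-ups use that baseline as comparator, so this change would enter a planned biochemical result in synbiotic and placebo groups alike. At stake is the reading of within-group GCF change, which the SAP does not label as descriptive.

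**Working it through.** **The plan's own figure.** The documents give no figure for regression to the mean. The only planned numbers that enter are the group sizes: 15, or 20 after adding 5 for missing data. The 15 can be reproduced as a repeated-measures within-between interaction (4 groups, 3 times, f = 0.25, correlation 0.5 assumed): N = 60, power 0.954. The present point does not depend on it.

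**Assumed inputs, none in the documents.**
- k, the number of candidate regions from which the worst is chosen: 2 to 6.
- R, the reliability of a region's reading across visits: 0.5 to 0.7.
- r, the correlation between same-day clinical and GCF fluctuations: 0.3 to 0.6, with 0 as a check.
- Visit error either independent across regions or half shared across the mouth. A shared part cannot influence which region is chosen.

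The unit is the SD of a single region's reading within a person: stable variance R plus visit variance 1 − R, total 1.

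**Expected shift.** With E(k) the expected maximum of k standard normal values (0.56, 1.03 and 1.27 for k = 2, 4 and 6):
- independent errors: shift = r × (1 − R) × E(k)
- half the error shared: shift = r × [(1 − R)/2] ÷ √[R + (1 − R)/2] × E(k)

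| k | R | r | Error | Shift (SD) |
|---|---|---|---|---|
| 4 | 0.7 | 0.3 | independent | 0.3 × 0.3 × 1.03 = 0.09 |
| 6 | 0.5 | 0.6 | independent | 0.6 × 0.5 × 1.27 = 0.38 |
| 2 | 0.5 | 0.6 | independent | 0.6 × 0.5 × 0.56 = 0.17 |
| 6 | 0.5 | 0.6 | half shared | 0.6 × 0.25 ÷ √0.75 × 1.27 = 0.22 |
| 2 | 0.7 | 0.3 | half shared | 0.3 × 0.15 ÷ √0.85 × 0.56 = 0.03 |
| any | any | 0 | either | 0 |

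Simulated shifts agree, the largest being 0.39.

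**Friedman rejection when nothing truly changes** (simulation, n = 15 to 20, nominal 5%):
- 4 to 6 candidates, independent errors: about 6 to 31%.
- 2 candidates, or half the error shared: about 4 to 12%.
- r = 0: about 4 to 6%.
- Regions chosen at a separate earlier visit with independent fluctuations: shift 0.00 SD, rejection about 3 to 6.5% across runs.

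**Outside these ranges.** With stability of only 0.3, k = 6 and r = 0.6, the shift is 0.6 × 0.7 × 1.27 = 0.53 SD and rejection reaches 0.41 at n = 20. With stability of 0.9 the shift is at most about 0.08 SD and rejection at most about 0.09.

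**Pooled strips.** Pooling reduces noise but does not remove the shift. Pooling the worst 4 of 12 sites with fully independent errors gives 0.09 to 0.31 SD and 12 to 68% rejection. Pooling two of 4 sites with half the error shared (R = 0.6, n = 20) gives about 5 to 8%. The Protocol does not say how many sites were in contention, so neither case is a better guide than the ranges above.

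**Between groups.** With the same selection rule in all four groups (n = 20, r = 0.6; k = 4 with stability 0.3, and k = 6 with stability 0.6), Kruskal-Wallis rejection was 0.042 and 0.056. The mean difference in change was 0.002 and 0.010 SD, which is effectively zero.

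**The case against.** **The visit of selection is not explicit.** The Protocol says the regions were fixed at baseline but not whose readings drove the choice, and screening measurements already existed. If those were used, most of the problem is already avoided. This stands as a caveat. Same-visit selection remains the natural reading, because baseline is defined as day 0 and screening is described separately.

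**Within-group change cannot show a tablet effect anyway.** This stands, and it limits what is at stake. Debridement, hygiene training and plaque control are given to everyone. With no site selection at all, n = 20, reliability 0.6 and an assumed real fall of 0.5, 0.8 or 1.0 SD, Friedman rejects 56%, 92% or 99% of the time. No arm is untreated, so the no-change null behind the 5 to 31% describes no arm of this trial. The selection effect is an artefact added to a real change.

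**Sampling inflamed, fixed sites has a purpose.** It keeps sites consistent and should yield measurable fluid. That stands, and moving the choice to screening keeps most of it.

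**Stronger readings that the documents do not support.** A reader might infer that all GCF markers must fall and that within-group improvement is therefore overstated. Selection is on clinical signs, not cytokines, so a marker shifts only as far as its fluctuation follows those signs. IL-10 is among the markers and has no assured direction. A reader might also infer that smoker versus non-smoker comparisons of change are distorted. That would need site variability to differ by smoking status, on which the documents say nothing, and the SAP plans no test of that change.

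**Conclusion.** The point holds in a limited form and is one to consider rather than a necessary change. On the natural reading, one visit both selects the extreme regions and supplies their baseline value, and the planned Friedman tests take up whatever regression to the mean results.

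A material effect is possible but not demonstrated, since the size rests entirely on assumed k, R, r and error structure. It ranges from 0.03 to 0.39 SD and about 5 to 31% no-change rejection under the stated assumptions, and is nil at r = 0.

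The synbiotic-placebo difference within each smoking stratum is not biased: the same rule applies in both arms, before any tablet is taken, by an examiner who does not know the group.

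**What to change.** In the Protocol, Biochemical Analysis, state that the GCF regions are determined from the clinical measurements at the screening visit, and that the day-0 GCF sample from those fixed regions is the baseline. This costs one sentence and a record of the chosen regions at screening, with no extra visit or sample. The downside is that a region chosen at screening may no longer be the worst on day 0. The benefit is only partial if the two visits are very close together, because a transient flare may then span both. The Protocol gives no interval.

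If screening readings were in fact used, say so; nothing else on this point needs to change.

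If regions were already chosen on day 0, label the within-group Friedman GCF results in the SAP as descriptive. Base biochemical conclusions on the baseline-adjusted synbiotic-placebo difference within each smoking stratum. That needs an added analysis, since the planned Kruskal-Wallis tests compare values at each visit without baseline adjustment, but no new data.

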**Document Date: February 27, 2018**

## Statistical Analysis

The suitability of the normal distribution of the variables in our study was evaluated with graphical and Shapiro-Wilks test. The median (minimum, maximum) was used to display the descriptive statistics of variables identified as an abnormal distribution. Number (n) and percentage values were given to show the distribution of categorical variables like gender.

Kruskal-Wallis non-parametric analysis of variance was used to examine if there has been any discrepancy in the values of the clinical and biochemical measurements at baseline, 1st month and 2nd month. Bonferroni correction with the dual comparisons were made to determine the group causing variations in the variables found significant differences as result of Kruskal-Wallis test.

For comparing the clinical, biochemical and microbiological measurements at baseline, 1 month and 2 months in each group (T(+) T(-), C(+), C(-)) Friedman non-parametric repeated measures analysis of variance was used. Bonferroni correction double comparisons were made in variables determined statistically significant differences from the result of the Friedman test.

G\*Power pack program\*\*\* was used in order to determine the number of samples used in the study. For the width effect f: 0.25, type-I error probability  $\alpha$ :0.05, type-II error probability  $\beta$ : 0.05 and power: 0.95, at least 15 sampling units have been calculated to include in the study for each group. At least 5 subjects were added for each group considering the missing data that was deemed to occur during the course of follow-up. Sample size calculation was attempted based on the primary outcome measure.

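### The SAP plans tests and per-group summaries but no synbiotic-minus-placebo estimate or confidence interval, so the size and precision of the tablet effect would not be reported

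*SAP*

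**What the plan says.** The protocol's title states the question as "The Effect of Synbiotic Tablet Usage on the Clinical and Biochemical" parameters in smokers and nonsmokers with gingivitis. Under Study Design, participants are first divided by smoking status, and then "both groups in itself were randomly assigned again into two groups as test and control groups". That gives four groups: T(+), C(+), T(-) and C(-). Measurements are taken on days 0, 30 and 60.

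The Statistical Analysis section of the SAP contains the following:

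- **Summaries.** "The median (minimum, maximum) was used to display the descriptive statistics of variables identified as an abnormal distribution". Categorical variables get counts and percentages. No summary is stated for normally distributed variables.
- **Between groups.** A Kruskal-Wallis test of the values at baseline, month 1 and month 2, with Bonferroni-corrected pairwise comparisons for variables where that test is significant.
- **Within groups.** A Friedman test in each of the four groups, with the same conditional pairwise step.
- **Sample size.** Effect size f of 0.25, alpha 0.05, "and power: 0.95, at least 15 sampling units have been calculated to include in the study for each group". Then: "At least 5 subjects were added for each group considering the missing data that was deemed to occur during the course of follow-up".

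Neither document plans a difference between synbiotic and placebo, a contrast in change from baseline, or a confidence interval.

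**The concern.** A trial titled as measuring an effect should report that effect and how precisely it is known. The planned outputs do not supply this.

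- A Kruskal-Wallis result across four groups says whether the groups differ somewhere. It does not say by how much the tablet differs from placebo.
- Friedman tests look at change inside one group. Every participant also receives debridement, polishing and oral hygiene training, so within-group change mixes the effect of that care with the tablet's.
- A minimum and a maximum are each one participant's value, and their range tends to widen as the sample grows. Without further assumptions they give no standard error for a difference.
- The pairwise step is conditional. After a non-significant Kruskal-Wallis test the reader has four group summaries and no tablet-placebo comparison.

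What is at stake is the reading of a non-significant result. An interval shows whether it is informative or inconclusive; the planned outputs cannot. The stated power of 0.95 invites a reader to treat any null result as informative.

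**Working it through.** **Inputs.** From the SAP: f = 0.25, alpha = 0.05, power 0.95, 15 per group, at least 5 more per group (so at least 20). From the protocol: 4 groups, 3 visits. Assumed, because the documents do not give them: normal data with equal SD, correlation between visits rho = 0.5, sphericity (epsilon = 1). No outcome SD is given, so results are in SD units at a single visit.

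**1. Reproducing 15 per group.**

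- One-way ANOVA, 4 groups: lambda = f² × N. For power 0.95 this needs N = 280, or 70 per group. It does not give 15.
- Repeated-measures ANOVA, group-by-time interaction, 4 × 3: lambda = f² × N × 3/(1 − rho), with 6 and 2(N − 4) degrees of freedom. At N = 60, lambda = 0.0625 × 60 × 3/0.5 = 22.5, df = 6 and 112, power 0.954. At N = 56, power is 0.937. This gives 60, or 15 per group.
- The within-factor (time) test with rho = 0.3 also gives N = 60, but it carries no tablet-placebo difference.

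The SAP's figure therefore reproduces under repeated-measures models. It does not reproduce under a one-way comparison of groups at one visit.

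**2. Width of the missing interval.** Half-width = t(0.975, 2n − 2) × sqrt(2/n).

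- n = 15: 2.048 × 0.365 = 0.75 SD.
- n = 20: 2.024 × 0.316 = 0.64 SD.

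Simulated Hodges-Lehmann intervals on normal data are slightly wider: about 0.78 and 0.66 SD.

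**3. What f = 0.25 means as a tablet-placebo difference d.**

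- *One-way reading.* Both T groups are shifted by d. The SD of the four means is d/2, so d = 2 × 0.25 = 0.50 SD.
- *Interaction reading.* Groups are equal at baseline, and both T groups are shifted by d at both follow-ups. The centred group effects are ±1/2 and the centred time pattern is (−2/3, 1/3, 1/3). The mean squared interaction is d² × (1/4) × (2/9) = d²/18, so d = 0.25 × sqrt(18) = 1.06 SD. If the effect builds up linearly instead, the month 2 difference is 0.25 × sqrt(24) = 1.22 SD.

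**4. Consequences under each reading.** Pair power is from the noncentral t distribution with noncentrality d × sqrt(n/2). Kruskal-Wallis power is simulated on normal data at one visit, with the effect in both strata.

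| | d = 0.50, n = 15 | d = 0.50, n = 20 | d = 1.06, n = 15 | d = 1.06, n = 20 |
|---|---|---|---|---|
| One T-C pair, alpha 0.05 | 26% | 34% | 80% | 90% |
| One T-C pair, Bonferroni for 6 pairs | 9% | 13% | 53% | 71% |
| Four-group Kruskal-Wallis | about 29% | about 39% | about 92% | about 98% |
| 95% interval centred on zero | ±0.75, includes d | ±0.64, includes d | ±0.75, excludes d | ±0.64, excludes d |

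**The case against.** The strongest objection concerns what a null result would mean. A reader might infer that non-significance is likely even if the tablet works as planned, and that a null result could never exclude the planned effect. That follows only if f = 0.25 is read as 0.50 SD, and the one-way model behind that reading needs 70 per group, not 15. Under the interaction model that does reproduce 15, the Kruskal-Wallis test has about 92% power at 15 per group, and an interval centred on zero excludes the implied 1.06 SD. The SAP states no model, so neither reading can be asserted. This part of the objection stands.

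Three further points also stand:

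- 15 per group is the calculated minimum. At least 20 are planned, so 15 analysed means losing the whole allowance of five.
- A reader might infer that the report will contain nothing but p-values and medians, or that null results will be written up as showing no difference. The SAP also plans counts and percentages, and its group medians let a reader see a raw difference for non-normal variables. Neither document says how a null result will be worded.
- A rule tying conclusions to the planning effect could not be applied, because the primary outcome, its SD and the model are not stated.

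None of this supplies the missing estimate. Two medians side by side give no precision, and the objection concedes that no interval is planned.

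**Conclusion.** The point holds as a gap in what is estimated and reported. No synbiotic-minus-placebo estimate or confidence interval is planned, and after a non-significant Kruskal-Wallis test no tablet-placebo comparison is given. The interval that is missing would be about ±0.75 SD within a stratum at 15 per arm and ±0.64 SD at 20, assuming normal data with equal SDs.

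Whether a null result would be informative is open. On the 0.50 SD reading it would not exclude the planned effect; on the 1.06 SD reading (rho = 0.5, epsilon = 1, constant shift at both follow-ups) it would. That dependence is itself a reason to report the interval, which shows what has been excluded without having to settle what f = 0.25 meant. The documents do not support a claim that the trial is bound to miss its planned effect. An interval adds no power; it changes only what can properly be concluded.

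**What to change.** Add to the Statistical Analysis section of the SAP:

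- For each outcome and each follow-up visit, report the Hodges-Lehmann T-C difference within each smoking stratum with its 95% confidence interval, whether or not the Kruskal-Wallis test is significant.
- Compute it on the same scale as the test it accompanies. The SAP compares values at each visit, so the estimate should use those values; an estimate on change from baseline could disagree with the test beside it.
- State that the intervals are not adjusted for multiplicity, or use Bonferroni-level intervals where they accompany Bonferroni-corrected tests. For six pairs the half-width rises to 2.839 × 0.365 = 1.04 SD at 15 per arm and 2.783 × 0.316 = 0.88 SD at 20.
- Base conclusions about non-significant comparisons on the interval, not on the p-value alone.

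Quartiles beside the minimum and maximum are optional. The cost is a few lines of SAP text and a little more standard software output, with no new data. The downside is that some results will have to be stated as inconclusive.
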